4.3 Concentration of $^{99\text{m}}\text{Tc}$ SPECT tracer

SPECT perfusion tracers are known to bind to red blood cells limiting the amount of tracer available to the myocardium for extraction [15]. Thus, concentration function used in the kinetic analysis is better represented by the plasma concentration of tracer instead of the whole blood concentration, as measured by the image-based methods used in this study. Correction for the plasma to whole blood ratio can be done by applying a correction curve. The correction curve has been determined with pig experiments but needs to be calibrated to humans. To estimate this correction, we will measure the whole-blood to plasma tracer concentration ratio at equilibrium (~30min post injection) which will then be used to rescale the full curve that was measured in the pig study. For this purpose, a 12ml blood sample (2x6ml) at 30min after the rest tracer injection and a 2nd 12ml (2x6ml) blood sample at 30min will be drawn after the stress injection. Whole blood and serum aliquots will be prepared and then measured in a well-counter to determine the concentration ratio.

5. Sample Size and Statistical Analysis

The sample size for the correlation studies (hypotheses 1 and 3) was calculated to provide a 95% confidence interval around $r=0.6$ that excludes $r=0.25$, which is considered the upper bound of no correlation. To obtain a difference in the z-transform of $r=0.6$ and $r=0.25$ of 1.96 requires an n of 24. A withdrawal rate of 10 to 15 % increases the number of patients required to 30 per group.

The sample size for the reproducibility study (hypothesis 2) is estimated to detect a 10% difference on background of 15% variability (assuming a SPECT MBF uncertainty similar to the high end of PET variability). This requires a sample size of 26 (power = 0.95; alpha =0.05). A withdrawal rate of 10 to 15 % increases the number of patients required to ~ 30 per group.

Adverse events will be listed on an individual basis. All safety variables and demographic data will be tabulated with descriptive statistics, if appropriate.

For the correlation studies global and regional MBF measurements acquired using SPECT and PET and calculated MFR will be correlated with Spearman correlation analysis. For the reproducibility study Bland-Altman plots will be used to determine significant bias and the coefficient of repeatability of global and regional MBF measurements acquired using SPECT and calculated MFR.

6. Study Population

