2. To determine the reproducibility of global and regional myocardial blood flow measurements and calculated myocardial flow reserve using SPECT and ^{99m}Tc -tetrofosmin in patients with an intermediate to high probability of CAD (Phase 2);
3. To evaluate the correlation of global and regional myocardial blood flow measurements and calculated myocardial flow reserve using SPECT and ^{99m}Tc -tetrofosmin to PET with Rb-82 or $^{13}\text{NH}_3$ in normal volunteers (Phase 3).

Hypotheses

1. The correlation of global and regional myocardial blood flow measurements and calculated myocardial flow reserve using SPECT to PET in patients with an intermediate to high probability of CAD will be $r > 0.6$ (Phase 1);
2. The test-retest reproducibility of global and regional myocardial blood flow measurements and calculated myocardial flow reserve using SPECT in patients with an intermediate to high probability of CAD will be within 10 to 15% (Phase 2);
3. The correlation of global and regional myocardial blood flow measurements and calculated myocardial flow reserve using SPECT to PET in normal volunteers will be $r > 0.6$ (Phase 3).

Study Type

Investigator-initiated, imaging research.

Study Design

For the Phase 1 correlation study, participants will undergo a standard clinical rest/stress PET study with either Rb-82 or $^{13}\text{NH}_3$ with a low dose CT and a rest/stress SPECT study with $^{99\text{m}}\text{Tc}$ within a 4 week period. Participants with CAD will be recruited from patients already referred for clinical SPECT or PET imaging and with an intermediate to high probability of CAD. Any participants who have an intervention or undergo a significant cardiac event during the 4 week interval will be excluded.

For the Phase 2 reproducibility study, participants will be recruited from patients already referred for clinical rest/stress SPECT imaging and with an intermediate to high probability of CAD. Participants will undergo a second rest/stress SPECT with $^{99\text{m}}\text{Tc}$ within a 4 week period. Any participants who have an intervention or undergo a significant cardiac event during the 4 week interval will be excluded.

For the Phase 3 correlation study, normal volunteer participants will undergo a standard rest/stress PET study with either Rb-82 or $^{13}\text{NH}_3$ with a low dose CT and a rest/stress SPECT study with $^{99\text{m}}\text{Tc}$ within a 4 week period.

Number of Participants

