Statistical Methods For the correlation studies, global and regional MBF measurements acquired using SPECT and PET and calculated MFR measurements will be correlated with Spearman correlation analysis. For the reproducibility study, Bland-Altman plots will be used to determine significant bias and the coefficient of repeatability of global and regional MBF measurements acquired using SPECT and calculated MFR.

Abbreviations

3D	three dimensional
ACC	American College of Cardiology
AC	attenuation correction
AE	Adverse Event
AV	atrial-ventricular
BMI	body mass index
CABG	coronary artery bypass graft
CAD	coronary artery disease
CRF	case report form
COPD	chronic obstructive pulmonary disease
CT	computed tomography
g	gram
ICH GCP	International Conference on Harmonization Good Clinical Practice
kg	kilograms
kVp	kilo-volt potential
MBF	myocardial blood flow
MBq	megabequerels
mcg	micrograms
mCi	millicurie
MFR	myocardial flow reserve
mg	milligrams
min	minute
mm	month
MRN	medical record number
mSv	milliseverts
¹³ NH ₃	Nitrogen-13-ammonia
NC	no correction
NYHA	New York Heart Association
OHSN-REB	Ottawa Health Science Network Research Ethics Board
PET	positron emission tomography
PCI	percutaneous coronary intervention
PHI	Personal Health Information
⁸² Rb	Rubidium-82 Chloride
SAE	Serious Adverse Event
SC	scatter correction
SPECT	single photon emission computed tomography
SOP	Standard Operating Procedures
^{99m} Tc	Technetium-99m
²⁰¹ Tl	Thallium Chloride
TOH	The Ottawa Hospital
UOHI	University of Ottawa Heart Institute
yyyy	year

1. Introduction

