1.2 Hypothesis

1. The correlation of global and regional myocardial blood flow (MBF) measurements and calculated myocardial flow reserve (MFR) using SPECT to PET in participants with an intermediate to high probability of CAD will be $r > 0.6$ (Phase 1);
2. The test-retest reproducibility of global and regional MBF measurements and calculated MFR using SPECT in participants with an intermediate to high probability of CAD will be within 10 to 15% (Phase 2);
3. The correlation of global and regional MBF measurements and calculated MFR using SPECT to PET in normal volunteers will be $r > 0.6$ (Phase 3).

2. Study Objectives

1. To evaluate the correlation of global and regional MBF and MFR measured using SPECT to that measured using PET in participants with an intermediate to high probability of CAD (Phase 1);
2. To determine the reproducibility of global and regional MBF measurements and calculated MFR using SPECT in participants with an intermediate to high probability of CAD (Phase 2);
3. To evaluate the correlation of global and regional MBF and MFR measured using SPECT to that measured using PET in normal volunteers (Phase 3).

3. Study Design

Phase 1:

Patients referred to the University of Ottawa Heart Institute Diagnostic Imaging Department for myocardial perfusion imaging (MPI), PET or SPECT, will undergo a clinically indicated rest/stress PET scan using either Rb-82 or $^{13}\text{NH}_3$. Research imaging will consist of a rest/stress SPECT scan with $^{99\text{m}}\text{Tc}$ completed with 4 weeks of the PET scan, occurring either before or after the PET scan.

Study end will be defined as the completion of both the PET and SPECT scans.

Phase 2:

Patients will undergo a clinically indicated rest/stress SPECT scan as referred. Research imaging will consist of a second rest/stress SPECT scan with $^{99\text{m}}\text{Tc}$ within 4 weeks of the clinical SPECT scan.

Study end will be defined as the completion of both SPECT scans.

Phase3:

Normal volunteers will undergo a rest/stress PET scan using either Rb-82 or $^{13}\text{NH}_3$ and a rest/stress SPECT scan with $^{99\text{m}}\text{Tc}$ completed within a 4 week period.

Study end will be defined as the completion of both the PET and SPECT scans.

4. SPECT and PET Imaging

4.1 $^{99\text{m}}\text{Tc}$ SPECT Imaging

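### Hypotheses 1 and 3 claim a SPECT–PET correlation above 0.6, but Section 5 sizes them only to exclude 0.25, and its n of 24 holds for a Pearson interval rather than the planned Spearman analysis

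*Combined protocol and SAP*

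**What the plan says.** Hypothesis 1 (Section 1.2) says that the correlation of global and regional flow and flow reserve "using SPECT to PET in participants with an intermediate to high probability of CAD will be $r > 0.6$ (Phase 1"). Hypothesis 3 makes the same prediction for healthy volunteers: "using SPECT to PET in normal volunteers will be $r > 0.6$ (Phase 3"). The synopsis repeats both. The matching objectives in Section 2 are milder: "To evaluate the correlation of global and regional MBF and MFR measured using SPECT to that measured using PET".

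Section 5 says that it sizes hypotheses 1 and 3, and gives the aim as "a 95% confidence interval around $r=0.6$ that excludes $r=0.25$, which is considered the upper bound of no correlation". The calculation is one sentence: "To obtain a difference in the z-transform of $r=0.6$ and $r=0.25$ of 1.96 requires an n of 24". Then: "A withdrawal rate of 10 to 15 % increases the number of patients required to 30 per group".

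On analysis, the synopsis says that flow and "calculated MFR measurements will be correlated with Spearman correlation analysis", and Section 5 says the same in substance. Neither place gives a decision rule, an interval method, or the role of 0.6 (expected value, threshold for the estimate, or threshold for a confidence limit).

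**The concern.** The value 0.6 does two jobs. In the hypotheses it is the value to be exceeded. In Section 5 it is the value assumed to be observed, and the value to be ruled out is 0.25. These are different claims, and the same data can satisfy one and not the other. At n=30, an observed r of 0.57 excludes 0.25 with a Pearson interval (0.560 is enough) yet falls short of 0.6. An observed 0.61 passes 0.6 on its face while the data remain compatible with a correlation near 0.3.

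Without a stated rule, an estimate just above 0.6 could be reported as confirming hypotheses 1 and 3, and the choice of standard could be made after the data are seen. There is also a smaller mismatch: the sizing formula is for a Pearson correlation and the planned analysis is Spearman.

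**Working it through.** **Inputs from Section 5:** planning value 0.6, value to exclude 0.25, two-sided 95% (1.96), withdrawal 10 to 15%, 30 enrolled per group. **Assumed, because the documents give no human SPECT–PET correlation:** the true r. Section 1.1 reports only pig SPECT against microspheres (0.75 to 0.83 for flow, up to 0.89 for flow reserve).

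**1. Reproduce the plan's n.** With Fisher's z and variance 1/(n−3):
- atanh(0.6) − atanh(0.25) = 0.6931 − 0.2554 = 0.4377
- n = 3 + (1.96/0.4377)² = 3 + 20.05 = 23.05, rounded up to 24. This matches.

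**2. What that n delivers.** The interval around an observed 0.6 is tanh(0.6931 ± 1.96/√(n−3)):
- n=24: 0.259 to 0.808
- n=27: 0.285 to 0.798
- n=30: 0.306 to 0.790

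By the same formula, a lower limit above 0.6 would need an observed r above 0.808 (n=24) or 0.790 (n=30).

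**3. Same criterion for Spearman.** Two usual variances are 1.06/(n−3) and (1+r²/2)/(n−3). At r=0.6 the second has numerator 1 + 0.36/2 = 1.18.
- 3 + 1.06 × 20.05 = 24.25, so 25
- 3 + 1.18 × 20.05 = 26.66, so 27

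Lower limit for an observed 0.6:

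| n | variance 1 | 1.06 | 1+r²/2 |
|---|---|---|---|
| 24 | 0.259 | 0.248 | 0.225 |
| 25 | 0.269 | 0.257 | 0.235 |
| 27 | 0.285 | 0.274 | 0.253 |
| 30 | 0.306 | 0.296 | 0.276 |

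At n=24 neither Spearman interval excludes 0.25.

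**4. Withdrawals.** 30 × 0.90 = 27, which is enough under either Spearman variance. 30 × 0.85 = 25.5, about 25, which is enough under 1.06 but not under 1+r²/2 (limit 0.235).

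**5. Chance that the lower limit exceeds 0.25.** Simulated Spearman on bivariate normal data, with one independent pair per participant. The ranges cover all three variances:

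| assumed true r | n=24 | n=30 |
|---|---|---|
| 0.60 | 43–51% | 55–61% |
| 0.70 | 72–78% | 83–87% |
| 0.75 | 84–88% | 93–95% |

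**6. Compare with a rule of observed r > 0.6.** At a true r of 0.5 that rule passes about 25% of the time at n=24 and 23% at n=30. The lower-limit rule passes 21–27% at n=24 and 28–33% at n=30. The two rules are close at n=24, and the lower-limit rule is slightly looser at n=30.

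**The case against.** The best defence is that 0.6 was meant as the expected estimate. An interval is drawn around an observed value, and at n=24 an observed Pearson r of 0.594 already excludes 0.25. An estimate above 0.6 is therefore almost exactly what satisfies Section 5, and on this reading hypotheses and sizing agree. The objectives only evaluate the correlation, and the protocol nowhere says that excluding 0.25 establishes 0.6. This is a fair reading, but no section states it, and the match is with the Pearson interval. If it is what was meant, saying so is most of the remedy.

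A second objection is that the restated rule decides little differently. That stands (step 6). The benefit lies in what a passing result is said to show. A third is that a criterion on the Spearman correlation is incomplete when the plan covers global and regional values, rest and stress, corrected and uncorrected images, and two software packages. That also stands, so the fix must name one correlation.

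A reader might go further and infer that the study should have been sized to test against 0.6 and is far too small. The documents do not support this. No passage plans a test with 0.6 as the null value, and the sizing is a reasonable precision target for the objectives as worded. Nor do the chances of about one half at a true r of 0.6 show a failed design, because the true r is unknown and the planned n serves the 0.25 criterion well from about 0.7 upward.

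**Conclusion.** The point holds as a mismatch between the stated claim and the criterion used to size it, and it should be fixed. Meeting Section 5's criterion supports r > 0.25. It does not support r > 0.6, since the interval around an observed 0.6 extends down to about 0.26 (n=24) or 0.31 (n=30) even with the narrower Pearson variance.

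The stated n of 24 is right for Pearson and one to three participants short for Spearman. The 30 enrolled absorb this at 10% withdrawal. At 15% they fall slightly short under the larger variance only.

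The interval limits and sample sizes rest on Fisher's z. The chances rest also on bivariate normal data, assumed true values and one pair per participant, so they do not carry over to several regions pooled within a participant. That a result near 0.6 would be over-read is a risk left open by the wording. The protocol does not say that it will be reported that way.

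**What to change.** In the synopsis, Section 1.2 and Section 5, for Phases 1 and 3:

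- State the criterion: the lower limit of the two-sided 95% confidence interval for the Spearman correlation exceeds 0.25. Call 0.6 the planning value.
- Name the one correlation it applies to, for example global flow reserve or global stress flow, with one image-correction method and one software package. Treat the other global and regional correlations as descriptive.
- Name the interval method: Fisher z with a stated Spearman variance, or bootstrap.
- Restate the evaluable n in Section 5 as 25 to 27 for that method, keep 30 enrolled, and note the small shortfall possible at 15% withdrawal.
- Give the chance of meeting the criterion over a range of assumed true r, as in step 5, and not at 0.6 alone.
- Say that an observed r near 0.6 will be reported with its interval and not presented as confirming r > 0.6.

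If the sponsor keeps r > 0.6 as the claim, state whether it is judged by the point estimate or by the lower limit, and give that rule's operating characteristics at the planned n.

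The cost is rewording in three places and choosing one primary correlation. Enrolment, procedures and the Spearman analysis are unchanged. The downside is a more modest formal claim.

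### Section 5 takes n=24 for Phases 1 and 3 from the Pearson z standard error although the analysis is Spearman; usual Spearman intervals need 24 to 27, and none is named

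*Combined protocol and SAP*

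**What the plan says.** Section 5 (Sample Size and Statistical Analysis) sets the target for hypotheses 1 and 3 as a 95% confidence interval around 0.6 that "excludes $r=0.25$, which is considered the upper bound of no correlation". The method is the z-transform: "To obtain a difference in the z-transform of $r=0.6$ and $r=0.25$ of 1.96 requires an n of 24". The allowance for losses follows: "A withdrawal rate of 10 to 15 % increases the number of patients required to 30 per group". Later in the same section the analysis is given: SPECT and PET flow measurements and "calculated MFR will be correlated with Spearman correlation analysis". The Statistical Methods entry of the synopsis agrees: "calculated MFR measurements will be correlated with Spearman correlation analysis".

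The document gives no variance or interval method for Spearman's coefficient, and no power for the correlation phases. Power (0.95) is stated only for the Phase 2 reproducibility calculation.

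**The concern.** The z-transform with variance 1/(n−3) belongs to Pearson's coefficient. Spearman's coefficient varies more on that scale, so a number that just meets the target for Pearson may not meet it for the statistic to be reported. This calculation is the only sizing basis for two of the three phases, which is 60 of the 90 planned participants. Because no interval is named, an analyst could also carry the Pearson formula over to Spearman's coefficient and report an interval that is slightly too narrow.

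A second feature lies beside this one. The calculation places the observed coefficient at 0.6 and has no power term, so it does not say how likely exclusion of 0.25 is.

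**Working it through.** **Inputs, all from Section 5:** expected coefficient 0.6; value to exclude 0.25; multiplier 1.96; stated n 24; 30 enrolled per group; 10 to 15% withdrawal.

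**Step 1: reproduce the plan's figure.** atanh(0.6) − atanh(0.25) = 0.6931 − 0.2554 = 0.4377. With standard error 1/√(n−3), n = 3 + (1.96/0.4377)² = 23.05, rounded up to 24. The lower limit is tanh(0.6931 − 1.96/√21) = 0.259 at n=24 and 0.2495 at n=23. The arithmetic is right for Pearson.

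**Step 2: repeat with Spearman variances on the same scale.**
- Fieller, 1.06/(n−3): n = 3 + 1.06 × 20.05 = 24.25, so 25.
- Bonett-Wright, (1 + r²/2)/(n−3), factor 1.18 at r=0.6: n = 3 + 1.18 × 20.05 = 26.66, so 27.
- Caruso-Cliff, 1/(n−2) + |z|/(6n + 4√n): smallest n is 24.

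Lower 95% limit around 0.6, by evaluable n:

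| n | Pearson | Fieller | Caruso-Cliff | Bonett-Wright |
|---|---|---|---|---|
| 24 | 0.259 | 0.248 | 0.2508 | 0.225 |
| 25 | 0.269 | 0.257 | 0.260 | 0.235 |
| 26 | 0.277 | 0.266 | 0.268 | 0.244 |
| 27 | 0.285 | 0.274 | 0.276 | 0.253 |
| 30 | 0.306 | 0.296 | 0.296 | 0.276 |

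**Step 3: apply the planned losses.** 30 × 0.90 = 27 and 30 × 0.85 = 25.5, so 25 to 27 remain. Over that range Fieller and Caruso-Cliff exclude 0.25 throughout. Bonett-Wright excludes it at 27 but not at 25 or 26. In the other direction, 25/0.85 = 29.4, so 30 enrolled is enough. 27/0.90 = 30 is just enough, and 27/0.85 = 31.8 would need 32.

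**Step 4: coverage.** Simulation with bivariate normal data and a true Spearman coefficient of 0.6 (at least 60,000 replicates per n, simulation error about 0.1 percentage point) gives coverage of about 94% for the Pearson formula, 94.7% for Fieller, 94.5% for Caruso-Cliff and 95.6% for Bonett-Wright.

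**Step 5: chance that the interval excludes 0.25, same simulation.**

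| True Spearman | n | Fieller | Bonett-Wright |
|---|---|---|---|
| 0.6 | 24 | 48% | 43% |
| 0.6 | 25 | 50% | 46% |
| 0.6 | 27 | 54% | 49% |
| 0.6 | 30 | 59% | 55% |
| 0.7 | 27 | 81% | 78% |

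**The case against.** The strongest reply is that the plan enrols 30, not 24. Since 24/0.85 rounds up to 29, there is already some slack, and at the planned losses two of the three Spearman intervals meet the target throughout. Even at n=24 Fieller misses by less than 0.003, and Caruso-Cliff does not miss. This stands. A reader might infer from the mismatch that the sizing property is lost for both phases. The documents do not support that: the property fails at the planned enrolment only under Bonett-Wright, and only when losses exceed 10%.

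It can also be said that 27 is no more correct than 25, since Fieller's coverage is about as close to 95% as Bonett-Wright's, from the other side. That stands too. The choice belongs to the investigators, but it has to be made and written down.

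On the exclusion probability, a reader might infer that the plan promises near-certain exclusion of 0.25, or that Spearman's coefficient causes the roughly even odds. Neither follows. Section 5 describes an interval around 0.6 and claims no power for these phases. A Pearson analysis at n=24 with a true Pearson coefficient of 0.6 would exclude 0.25 only about 54% of the time. The even odds come from sizing on an observed 0.6. What survives is that Section 5 leaves this conditional basis unstated, next to a Phase 2 calculation that does quote power.

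**Conclusion.** The point holds as a mismatch between sizing formula and analysis, with a modest effect. The evaluable number of 24 is correct for Pearson and 0 to 3 short for Spearman, depending on an interval that the plan does not name. Enrolment of 30 covers the shortfall fully under Fieller or Caruso-Cliff at 10 to 15% loss, and under Bonett-Wright up to 10% loss. Reusing the Pearson formula would cost about one percentage point of coverage. The hypotheses themselves are not affected.

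Assumptions: the planning value of 0.6 is read as a Spearman coefficient, and the simulated figures rest on bivariate normal data. If 0.6 were instead a Pearson value under normality, the matching Spearman value would be (6/π)·asin(0.3) = 0.582. The required number would then rise to 28 (Fieller, 27.2 before rounding) or 30 (Bonett-Wright, 29.7).

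**What to change.** In Section 5, with no added participants:

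1. Name one Spearman-valid 95% interval as the one to be reported, in place of the Pearson formula.
2. Restate the evaluable number to match. Either 25 with Fieller, which 30 enrolled meets at about 15% loss, or 27 with Bonett-Wright, which 30 enrolled meets at up to 10% loss.
3. State that the sizing is conditional on an observed coefficient of about 0.6, and give the chance of excluding 0.25 at a true Spearman coefficient of 0.6 for the interval chosen: about 50% at 25 and 59% at 30 (Fieller), or about 49% at 27 and 55% at 30 (Bonett-Wright). Add that with 27 evaluable it rises to about 78 to 81% at a true coefficient of 0.70.

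The cost is a wording change to Section 5. The downside is that the stated figures look slightly less favourable than they do now.

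### Phase 2 claims that repeat SPECT results are close, but it is sized to detect a difference and judges bias only by significance, which cannot show that bias is small

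*Combined protocol and SAP*

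**What the plan says.** Section 1.2 and the synopsis put hypothesis 2 as a statement of closeness: reproducibility "will be within 10 to 15% (Phase 2"). The tolerance is not attached to any statistic, such as the mean difference, within-patient SD, limits of agreement or coefficient of repeatability.

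Section 5 gives the basis for the Phase 2 sample size. It "is estimated to detect a 10% difference on background of 15% variability", the 15% being justified by "assuming a SPECT MBF uncertainty similar to the high end of PET variability". The result is a "sample size of 26 (power = 0.95; alpha =0.05"), raised to about 30 for withdrawals of 10 to 15%. Neither the sidedness of the test nor the kind of SD (paired difference or single scan) is stated.

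For the analysis, Section 5 says that "Bland-Altman plots will be used to determine significant bias and the coefficient of repeatability", and the synopsis (Statistical Methods) repeats this. Neither place gives a margin, a confidence-interval rule, or an acceptance limit for the bias or the coefficient.

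**The concern.** A claim of closeness is supported by ruling out differences that are too large. A test of zero difference does something else: it can show that a difference exists, but failing to show one is not evidence of its absence. Noise also acts in the wrong direction, because a larger SD makes a real bias less likely to reach significance.

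At stake is the bias half of the reproducibility conclusion. With significance as the only stated criterion for bias, a report could describe the SPECT measurement as free of significant test-retest bias when the data cannot exclude a bias as large as the one the study was sized to find.

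**Working it through.** **Inputs.** From Section 5: difference 10%, variability 15%, n = 26, power 0.95, alpha 0.05, withdrawal 10 to 15%. Assumptions: differences are on a percentage scale and roughly normal; 15% is the SD of the paired difference. If 15% is the SD of a single scan, the SD of the difference is 15 × √2 = 21.2%. An SD of 30%, twice the plan's figure, is included as a stress case.

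**1. The plan's own figure.** One-sample test of the mean paired difference against zero, one-sided 0.05:

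- Normal approximation: (15 × (1.645 + 1.645) / 10)² = 24.3, so 25.
- Exact noncentral t: power 0.944 at n = 25 and 0.952 at n = 26. The stated 26 is reproduced.
- Two-sided 0.05: power at n = 26 is 0.904, and 32 would be needed for 0.95.
- Withdrawals: 26/0.90 = 28.9 and 26/0.85 = 30.6, consistent with about 30.

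So 26 is the size of a test for a difference, and it reproduces only one-sided.

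**2. How often a true 10% bias is missed at n = 26.** Two-sided 0.05, critical value 2.060 on 25 df. Noncentrality = 10 / (SD/√26). The probability of non-significance is approximately Φ(2.060 − noncentrality); exact noncentral-t values are in the last column.

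| SD of difference | SE | Noncentrality | Non-significant (exact) |
|---|---|---|---|
| 15% | 2.94 | 3.40 | 10% |
| 21.2% | 4.16 | 2.40 | 36% |
| 30% | 5.88 | 1.70 | 63% |

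Sidedness is not stated. With a one-sided test in the direction of the bias (critical value 1.708) the figures are 5%, 24% and 50%, so the pattern is the same. With no true bias, the two-sided result is non-significant in 95% of studies whatever the SD.

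**3. What the repeatability statistic would show.** Coefficient of repeatability = 1.96 × SD of the difference: 29.4% at SD 15% (95% CI about 23% to 41% at n = 26), 41.6% at 21.2% and 58.8% at 30%. The within-patient SD at a difference SD of 15% is 15/√2 = 10.6%. The same data are therefore inside or outside 10 to 15% depending on which statistic is meant.

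**4. An interval rule for bias.** Conclude no material bias only if the 90% CI lies inside ±10%. At n = 26 and SD 15% the half-width is 1.708 × 15/√26 = 5.0%. Power at zero true bias is approximately 2Φ(10/SE − 1.708) − 1; exact values are:

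| SD of difference | n | True bias | Passes the ±10% rule |
|---|---|---|---|
| 15% | 26 | 0 | 0.90 |
| 15% | 30 | 0 | 0.945 |
| 15% | 26 | 5% | 0.50 |
| 15% | 26 | 10% | 0.05 |
| 21.2% | 26 | 0 | 0.51 |
| 30% | 26 | 0 | 0.08 |

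Under this rule noise lowers the chance of a favourable conclusion. Keeping 0.95 power at zero bias would need 31 evaluable patients at SD 15%, or 60 at SD 21.2%.

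**The case against.** The strongest reply is that Section 5 contains no success rule. It never says that a non-significant bias establishes hypothesis 2, and the same sentence plans the coefficient of repeatability, which rises in step with the noise. A reader might infer that noisy data would simply pass. The documents do not support that: an SD of 30% would appear as a coefficient of about 59% beside the bias result. What remains is that the coefficient has no acceptance limit, so nothing in the plan makes a poor value count against the hypothesis, and significance is the only stated criterion for bias.

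A reader might also infer that the plan flags methods that satisfy hypothesis 2, since at SD 15% a two-sided test finds a true 10% bias in 90% of studies. That requires the 10 to 15% to be a limit on mean bias. The text speaks of reproducibility and does not mention bias there. If the tolerance concerns repeatability, a systematic 10% shift does not meet the hypothesis merely by being 10%, and flagging it may be right.

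It can fairly be said, too, that the ±10% rule is strict. It rejects a true 10% bias 95% of the time and a true 5% bias about half the time. That is a real cost. It is not inconsistent, because here ±10% stands for the difference that the plan chose to detect and not for the tolerance in hypothesis 2.

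Finally, the arithmetic behind 26 is not wrong. It answers a different question from the one hypothesis 2 asks.

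**Conclusion.** The mismatch holds. Hypothesis 2 asserts closeness, while Phase 2 is sized to detect a 10% difference and bias is judged by significance alone. At n = 26 and two-sided 0.05, the chance that a true 10% bias is non-significant is 10%, 36% or 63% at SDs of the paired difference of 15%, 21.2% or 30%. The first two are the two readings of the plan's own 15%; the third is a stress case with no support in the documents.

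The point is limited to the bias conclusion and to the undefined tolerance. It does not show that the plan would accept noisy data overall, that a 10% bias meets hypothesis 2, or that 26 was miscalculated. The percentages rest on approximate normality and a percentage scale for the differences. It is worth correcting before analysis because it affects one of three stated hypotheses and can be put right in the text.

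**What to change.** In Section 5 and in the synopsis under Statistical Methods:

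1. Replace the significance criterion for Phase 2 bias with the mean test-retest difference and its 90% CI, reported whatever the result. Conclude no material bias only if the interval lies inside ±10%, the difference that the plan itself chose to detect.
2. Judge the 10 to 15% of hypothesis 2 separately. Name the repeatability statistic it applies to, give the limit, and report the statistic with its CI. If the coefficient of repeatability is meant, note that the planning SD of 15% already implies about 29%.
3. State whether 15% is the SD of the paired difference or of a single scan.
4. Restate the basis for n = 26 as about 0.90 power for the bias rule at zero true bias if 15% is the SD of the paired difference (about 0.945 if all 30 are evaluable), or about 0.51 if it is per scan.

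The cost is a few sentences, with no added patients or scans. The stated power falls from 0.95 to about 0.90, and a method with a true 5% bias would pass only about half the time. If the 15% proves to be per scan, the bias conclusion is weakly powered at this size, and the protocol should say so.

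### Section 5's 0.95 power for Phase 2 at n = 26 holds only for a one-sided test with 15% as the SD of the paired difference; the protocol states neither condition

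*Combined protocol and SAP*

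**What the plan says.** The Phase 2 sample size is in protocol Section 5 (Sample Size and Statistical Analysis). The aim is to "detect a 10% difference on background of 15% variability (assuming a SPECT MBF uncertainty similar to the high end of PET variability"), and the 15% is explained only by the remark in that parenthesis. The result follows: "This requires a sample size of 26 (power = 0.95; alpha =0.05"). An allowance of 10 to 15% for withdrawals takes this to about 30.

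The design is paired. Under Phase 2 in Section 3, each patient has a clinical SPECT study, and "Research imaging will consist of a second rest/stress SPECT scan" within 4 weeks. On analysis, Section 5 says: "For the reproducibility study Bland-Altman plots will be used to determine significant bias and the coefficient of repeatability".

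Hypothesis 2 (Synopsis and Section 1.2) expects SPECT test-retest reproducibility within 10 to 15%, without saying which statistic that range refers to. Section 5 does not name the test behind the 26, does not say whether alpha is one- or two-sided, and does not say whether the 15% belongs to one scan or to the difference between two.

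**The concern.** A Bland-Altman assessment of bias is inference on the mean within-person difference, so the SD that sets its power is the SD of that difference. The wording in Section 5 can be read as the error of a single blood-flow measurement. Two scans each carry such an error, and if the errors are independent the SD of their difference is larger by a factor of √2. Sidedness also matters: a second scan can read higher or lower than the first, yet the printed power turns out to need a one-sided alpha.

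In a reproducibility study, finding no significant bias is the favourable result. If power for a 10% shift is well below 0.95, such a finding says less than Section 5 leads the reader to expect. On the least favourable combination considered here (per-scan error, independent errors, two-sided test), a true 10% shift would be missed about 36% of the time (1 − 0.64), against the 5% implied by the plan.

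**Working it through.** **Inputs from Section 5:** difference δ = 10%, variability 15%, n = 26, power 0.95, alpha 0.05. **From Section 3:** two SPECT studies per participant, hence paired data. **Assumed:** differences expressed as percentages and roughly normal.

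**Method.** One-sample t-test on paired differences. Power comes from the noncentral t distribution with n − 1 degrees of freedom and noncentrality δ / (SD_diff / √n).

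**1. Reproducing the printed figure.** With SD_diff = 15%, the noncentrality is 10 / (15 / √26) = 3.40.

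- One-sided alpha 0.05: power 0.952, and 26 is the smallest n that reaches 0.95. This matches the plan.
- Two-sided alpha 0.05: power 0.904; 0.95 would need n = 32. (26 is the smallest n for a two-sided power of 0.90.)
- Two independent groups with SD 15%, normal approximation: 49 (one-sided) or 59 (two-sided) per group. No match.

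So 15% was used directly as the SD of the difference, and the power of 0.95 is a one-sided figure. The withdrawal allowance is consistent: 26 / 0.90 = 28.9 and 26 / 0.85 = 30.6, or about 30.

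**2. If 15% is the error of one scan.** With correlation ρ between the two scan errors, SD_diff = 15% × √(2(1 − ρ)). Power at n = 26 for a 10% difference:

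| Meaning of the 15% | SD_diff | One-sided | Two-sided |
|---|---|---|---|
| SD of the paired difference | 15.0% | 0.952 | 0.904 |
| Per scan, ρ = 0.5 | 15.0% | 0.952 | 0.904 |
| Per scan, ρ = 0.25 | 18.4% | 0.854 | 0.760 |
| Per scan, ρ = 0 (independent) | 21.2% | 0.756 | 0.637 |

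With all 30 evaluable, two-sided power is 0.942 at SD_diff 15% and 0.704 at 21.2%; the one-sided values are 0.973 and 0.810.

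**3. Separating the two effects.** The √2 factor alone takes power from 0.95 to 0.76 one-sided, or from 0.90 to 0.64 two-sided. The change of sidedness alone takes it from 0.95 to 0.90 at SD_diff 15%.

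**4. Difference detectable with 0.95 power, n = 26, two-sided.** At SD_diff 21.2% it is 15.6%. Power depends only on δ / SD_diff, so at 15% it is 15.6% / √2 = 11.0%.

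**5. Expected half-width of the 95% confidence interval for the bias, n = 26.** This is t(0.975, 25) × SD_diff / √26, with t = 2.06:

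- SD_diff 15%: 2.06 × 2.94 = 6.1 percentage points.
- SD_diff 21.2%: 2.06 × 4.16 = 8.6 percentage points.

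**The case against.** A reader might infer that the planners took a single-scan error and forgot the √2, so that power simply falls to 0.64–0.76. The documents do not support that. Section 5 never says that the 15% is per scan. It also calls the figure variability and ties it to PET variability, which could well be a test-retest quantity. The calculation is labelled as serving Hypothesis 2, whose 10 to 15% range is explicitly about test-retest reproducibility. That n = 26 comes out exactly with 15% as the paired SD is also what one would see if the planners meant a paired SD and computed correctly. It shows how the figure was used, not that it was misused. The deciding fact is the PET source figure, for which Section 5 gives no citation.

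A second tempting reading sets the two-sided 0.64 against the printed 0.95 and blames the whole gap on the √2. Part of that gap is the change from a one-sided to a two-sided test.

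It is also fair to say that the planned Bland-Altman bias and coefficient of repeatability are computed in the same way whatever the 15% means.

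All of this stands, and it makes the √2 loss conditional. It does not rescue the printed statement. Calling the 15% an uncertainty in SPECT flow leans towards a per-scan error, and Hypothesis 2 does not define its range as an SD of differences. Correlated scan errors restore the figure only if the correlation reaches 0.5, which the plan does not claim. Even on the paired-SD reading, two-sided power at n = 26 is 0.90.

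**Conclusion.** The point holds in conditional form. Section 5 rests its Phase 2 size on a power of 0.95 that needs two conditions it does not state: that 15% is the SD of the paired difference, and that the test is one-sided. For a two-sided test, which suits a bias that may go in either direction, power for a 10% difference at n = 26 is 0.90 if 15% is the paired SD and 0.64 if it is a per-scan error with independent errors (0.76 at correlation 0.25). The one-sided counterparts are 0.95, 0.76 and 0.85. Which row applies cannot be decided from the documents, so the finding is an undefined input and an unstated sidedness, not a proven slip in the calculation. The figures assume 26 evaluable participants and approximately normal percentage differences. Nothing here requires more participants; what needs correcting is the claim about what 26 can show.

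**What to change.** Keep enrolment at 30. The sponsor should check its PET source, confirm whether the 15% is a per-scan error or the SD of the paired difference, and restate Section 5 for a two-sided paired test at alpha 0.05, using whichever text applies:

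- **If it is the paired SD:** *The SD of the paired test-retest difference is assumed to be 15%; 26 evaluable participants give 90% power for a 10% mean difference, and 95% power for about 11.0%.*
- **If it is per scan:** *The per-scan error is assumed to be 15%, with independent errors, so the SD of the difference is 21.2%; 26 evaluable participants give about 64% power for a 10% mean difference, and 95% power for about 15.6%.*

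In either case, add that the Phase 2 bias will be reported with its 95% confidence interval (expected half-width about 6.1 or 8.6 percentage points respectively), so that a non-significant bias is read alongside its precision.

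The cost is a look at the source and a few sentences, with no added participants, scans or procedures. The downside is that the stated power, or the difference the study can detect, becomes less favourable.
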